Participants in both groups will be assessed by a physiotherapist on five occasions (Figure 1): at base-line, four weeks into the treatment period, and then 1, 6 and 12 months after healing (when treatment is ended). For the 4 week into treatment and 1 month post-treatment assessments, a visit window of ± 1 week will be used. For the 6 and 12 months post-treatment assessments, a visit window of ± 1 month will be used. Standardized and validated instruments and assessment methods will be used for the data collection (Table 1).

Aim 1: Ulcer healing (primary end point)

Primary outcome measure is ulcer healing after 12 weeks of treatment, defined by the Food and Drug Administration (FDA) as full skin epithelization of the ulcer, confirmed by a second observation 14 days later.¹⁸ The cast technicians will assess ulcer healing in both the intervention group and control group. They will also photograph the ulcer and healed skin so a person blinded to group allocation can assess ulcer healing afterwards.

Aim 2: Adverse events during treatment (secondary end points)

Adverse events that are judged to be related to the offloading devices (shoe or TCC) will be classified as adverse device effects (ADE) and serious adverse device effects (SADE).³² ADE include, but are not limited to, skin abrasions, blisters, sleep disturbances, issues with gait and balance, etc. SADE include, but are not limited to, new foot ulcers that result in amputation (major amputation = above ankle, minor amputation = below ankle), sepsis, etc.

Adverse events that are not related to the offloading devices are classified as adverse events (AE) and serious adverse events (SAE).³² AE include, but are not limited to, skin abrasions, new foot ulcers on the contralateral foot and not related to the device, etc. SAE include, but are not limited to, death, amputation, onset of acute Charcot foot, sepsis, etc. (not related to the offloading device). However, in accordance with previous studies on this patient population, the investigators choose not to include all AE and SAE as the patient population suffers from multiple co-morbidities and therefore a high incidence of illness and hospital admissions unrelated to the DFU and offloading devices can be expected.³³ Therefore, all

ADE and SADE will be assessed, but only certain types of AE and SAE that are of particular interest, such as, amputation, death and onset of acute Charcot foot.

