For working patients, casting often means sick leave from work, but casting can also be difficult for older patients with impairments of gait and balance. For patients where TCC is contraindicated or not tolerated, guidelines recommend removable offloading devices despite it is well known that these devices are not very effective.⁸ In practice, this means that many patients do not receive effective treatment. Another problem is that many patients get new foot ulcers after treatment with TCC,¹² in part because adherence to using therapeutic footwear after healing is lower than desirable.¹³

Sealed therapeutic shoe as alternative treatment

The investigators have developed a new treatment concept, sealed therapeutic shoe, which potentially can fill the need for effective ulcer treatment without limiting ambulatory activity with its associated negative consequences for physical, mental and social health, and to a lower cost, resulting in fewer obstacles for clinical use.

The concepts include therapeutic shoes with custom-made insoles, where the new part is how the insole is optimized to offload the ulcer from mechanical loading and that the shoe is "sealed" with a soft plastic strap and is used day and night, like a cast, and is only removed when changing the ulcer dressings. The ulcer is thereby offloaded but the person is free to ambulate and work as usual, and no cast changes are necessary. In addition to effective ulcer treatment and fewer side-effects the investigators hope that the

positive experience of that high adherence to using therapeutic shoes results in healing will lead to higher adherence after healing, and thereby reduction of the risk of ulcer recurrences in the future. The method to offload foot ulcers was first tested in a case-study, where the investigators found that the shoe and insole effectively offloaded the ulcer.¹⁴ After this, the whole sealed shoe concept was evaluated in a feasibility study¹⁵ on seven people with DFU. All ulcers healed and complications were few. The investigators are now going to evaluate the effects of sealed therapeutic shoes compared to gold standard treatment, that is, TCC.

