2.3 SAMPLE SIZE

The sample size calculation was performed using <http://powerandsamplesize.com/Calculators/Compare-2-Proportions/2-Sample-Non-Inferiority-or-Superiority>. Primary outcome is proportion of healed ulcers after 12 weeks of treatment. Based on the literature and our feasibility study the proportion of healed ulcers after 12 weeks treatment is estimated to 90% with sealed shoe or TCC.^{15, 16} If accepting $p=0.05$, a statistical power of 80% and a non-inferiority limit of 10%, 112 participants are

needed. To compensate for attrition of participants during the long-term follow up of secondary outcomes, the aim is to recruit 150 participants. The participants will be randomized to treatment with sealed therapeutic shoe or TCC. However, if it turns out that it is too difficult to recruit 150 participants, the recruitment of participant will end when the primary end point (healing at 12 weeks) has been observed for 56 participants per group, giving a total of 112 which fulfils the sample size calculation.

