2.7 TIMING OF OUTCOME ASSESSMENTS

Table 1 below lists outcomes and time points for assessments (base-line, 4 weeks into treatment, and 1, 6 and 12 months after treatment end). For the 4 week into treatment and 1 month post-treatment assessments, a visit window of ± 1 week will be used. For the 6 and 12 months post-treatment assessments, a visit window of ± 1 month will be used.

Table 1. Overview of variables and assessment methods.

Variable (scale level: nominal=N, ordinal=O, interval=I)	Assessment method	Assessment occasion				
		Treatment period		Follow-up after treatment end		
		Base- line	4 weeks	1 month	6 months	12 months
Ulcer healing (N)	Clinical observation + blinded photo	X	X	X		
Skin complications (N)	Clinical observation + blinded photo	X	X	X		
Glycemic control (I)	Blood sample (HbA1c) ^a	X	X	X	X	X
BMI (I)	Measurement of weight and height	X	X	X	X	X
Gait function (I)	10 meter walk test ^{b 17}	X	X	X	X	X
Gait function (I)	Timed up and go ^{b 18}	X	X	X	X	X
Balance (O)	Berg balance scale ^{b 19}	X	X	X	X	X
Muscle atrophy (I)	Calf circumference ^{a 20}	X	X	X	X	X
General quality of life (O)	RAND-36 ^{c 21} , EQ-5D-5L ^{c 22}	X	X	X	X	X
Disease-specific quality of life (O)	DFS-SF ^{c 23}	X	X	X	X	X
Physical activity (I)	ActivPAL ^{d 24}	X	X	X	X	X
Physical activity (O)	National Board of Health and Welfare's indicator questions ²⁵	X	X	X	X	X
Bone mass density (I)	DXA ^e (heel bone)	X		X	X	X
Locus of control (O)	Questions from MHLC-C ^{c 26}	X		X	X	X
Ankle range of motion (I)	Goniometer ^{a 27}	X		X	X	X
Ankle strength (I)	Dynamometer ^{a 28}	X		X	X	X
Adherence to therapeutic shoes (O)	Questions from Q-TFA ^{c 29}	X		X	X	X
Treatment satisfaction (O)	Visual analogue scale ^c		X	X		
New ulcers, amputations, death, Charcot foot (N)	Patient file and self-report ^c				X	X
Health care consumption (O) ^f	Patient administration systems and self-report ^c			X	X	X
Sick leave from work (I) ^f	Self-report, ^c Swedish Social Insurance Agency's system			X	X	X

^aStandardized method, ^bfunction test, ^cquestionnaire, ^dactivity monitor, ^eDual-energy X-ray absorptiometry ^ffor the of health-economic analysis.

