6.1.2 ANALYSIS OF THE SECONDARY ENDPOINT(S)

The secondary analyses are not dependent on the findings of the primary endpoint. No adjustment for Type 1 errors will be used as only one or a few statistical tests will be conducted for each secondary endpoint.

The secondary endpoints are time to healing and measures listed in Table 1. Each secondary endpoint is measured between one and five occasions during the study. The ITT dataset will be used for all analyses of secondary endpoints. Adjusted analyses will only be conducted for certain secondary endpoints that are of particular interest.

Time to healing will be compared between the study groups using survival analysis. Kaplan-Meier survival curves will be produced for the two study groups with median healing times and 95 % CI. Participants for whom the ulcer has not healed will be treated as censored and their date of trial exit or date of last available assessment will be used to calculate their duration in the trial. Hazard ratio with

95% CIs will be presented. Treatment effect will be explored using a Cox proportional hazards model including stratification factors (ulcer area and depth at baseline, periphery artery disease and infection grade) initially.

Survival analysis as above (but without adjustment) will also be used to compare ulcer recurrence after healing between the study groups. Recurrence rates at 12 months after healing will also be compared.

The analysis of the other secondary endpoints will be conducted according to scale level (nominal, ordinal or interval; Table 1) and compared at each time point (base-line, 4 weeks into treatment and 1, 6 and 12 months post-treatment) using the ITT dataset without adjustment for covariates: t-tests for ordinal and interval data if the assumptions of the t-test is fulfilled (normal distribution and equal variances), otherwise Wilcoxon rank sum test will be used. The Chi-squared test or generalized linear regression method will be used for nominal scale data. For each comparison both exact p-values and two-sided 95% CI will be reported.

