The health economic analysis will be a cost-utility analysis that compare the interventions (sealed shoe and cast): treatment costs, quality of life during and after treatment, sick leave from work, and health care consumption. Effects on quality of life will be assess with EQ-5D-5L and SF-36 that makes it possible to express effects on quality of life in terms of quality-adjusted life years. The perspective of the analysis will be societal and take effects from the treatment start to 12 month after treatment end into account. Questionnaires, patient administrative systems, and the Swedish Social Insurance Agency's system will be used as data sources.

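### The cost-utility window closes 12 months after each participant's own treatment end, so QALYs and costs cover unequal periods if mean treatment duration differs between arms

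*SAP*

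**What the plan says.** The health economic paragraph of SAP 6.1.2 plans a cost-utility analysis from a societal perspective. It covers treatment costs, quality of life, sick leave and health care use, and it will "take effects from the treatment start to 12 month after treatment end into account".

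The Protocol (Data collection) schedules the follow-up visits at baseline, at four weeks "and then 1, 6 and 12 months after healing (when treatment is ended"). SAP 2.7 anchors the visits in the same way: "base-line, 4 weeks into treatment, and 1, 6 and 12 months after treatment end". It adds: "For the 6 and 12 months post-treatment assessments, a visit window of ± 1 month will be used".

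Whether the arms differ in duration is left open. SAP 2.3 plans on equal healing: "the proportion of healed ulcers after 12 weeks treatment is estimated to 90% with sealed shoe or TCC". SAP 6.1.2 nevertheless makes duration a comparison: "Time to healing will be compared between the study groups using survival analysis". For participants who have not healed, that survival analysis supplies an end date: "their date of trial exit or date of last available assessment will be used to calculate their duration in the trial". The economic paragraph has no corresponding rule.

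**The concern.** The length of the economic window depends on time to healing, which is observed after randomisation and may be affected by the device. QALYs, health care costs and sick leave all accumulate with time. Under this window an extra week on treatment is added to a participant's total, whereas under a fixed horizon it would replace a week in the healed state. An arm that heals more slowly is therefore credited with more QALYs, and charged with more cost, partly because it is counted for longer. Randomisation does not prevent this, and a larger sample does not remove it.

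What is at stake is Aim 4, a two-sided comparison of health economic outcomes, and the part of the overarching aim that concerns lower cost. The primary endpoint is untouched.

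**Working it through.** The documents give no QALY result, utility, QALY standard deviation or treatment duration, so there is no figure of the plan to reproduce. The window rule comes from SAP 6.1.2 and the Protocol. The 90% healing rate, the 10-point limit and the 56 and 75 per arm (112/2 and 150/2) come from SAP 2.3. The rest is assumed and given as a range.

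**Bias formula.** Let f be the faster arm and s the slower arm. T is mean treatment weeks (under 52), u is utility during treatment, u_h is utility afterwards (the same in both arms), and d = T_s - T_f.
- SAP window, f minus s: (u_f·T_f - u_s·T_s)/52.
- Common 52-week horizon, f minus s: [(u_h - u_s)·T_s - (u_h - u_f)·T_f]/52.
- SAP window minus common horizon: -u_h·d/52. Utility during treatment cancels.

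Per week of difference: 0.6/52 = 0.0115, 0.7/52 = 0.0135 and 0.8/52 = 0.0154 QALY. If d = 0 the bias is 0.

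**Plausible values of d.** I assumed Weibull healing times with the proportion healed at week 12 held fixed. No section ends treatment at week 12, so durations are shown both restricted to 12 weeks and with extrapolated tails. The bias range runs from utility 0.6 with the smallest d to utility 0.8 with the largest, before rounding d.

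| Healed at week 12 | Durations | d in weeks, shape 2 to shape 1 | Size of bias, QALY |
|---|---|---|---|
| 90% vs 90%, same healing times | either | 0 | 0 |
| 90% vs 85% | restricted | 0.54 to 0.69 | 0.006-0.011 |
| 90% vs 85% | with tails | 0.71 to 1.11 | 0.008-0.017 |
| 90% vs 80% | restricted | 0.99 to 1.27 | 0.011-0.020 |
| 90% vs 80% | with tails | 1.37 to 2.24 | 0.016-0.035 |

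**Against precision.** The standard error of the difference is SD·√(2/n). With SD 0.15 and 75 per arm it is 0.0245; with SD 0.25 and 56 per arm it is 0.0472. At 90% versus 80%:
- restricted: 0.0114/0.0472 = 0.24 to 0.0196/0.0245 = 0.80 standard errors;
- with tails: 0.0159/0.0472 = 0.34 to 0.0345/0.0245 = 1.41 standard errors.

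**Sign.** The SAP window shows a QALY loss for the faster arm only if u_f/u_s < T_s/T_f. With u_h = 0.75:
- 8 versus 10 weeks, utility 0.65 during treatment in both arms: SAP window (5.2 - 6.5)/52 = -0.025; common horizon (1.0 - 0.8)/52 = +0.004. The sign reverses.
- 9 weeks at 0.70 versus 10 weeks at 0.60: SAP window (6.3 - 6.0)/52 = +0.006; common horizon (1.5 - 0.45)/52 = +0.020. The sign does not reverse.

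**Can a 52-week cut-off be reached with planned data?** The last visit falls 12 months after treatment end, give or take a month. Someone whose treatment ends before about week 4.3 and who is seen early in that window has no EQ-5D-5L at or after week 52. Under the 90% curves, 26% (shape 2) to 57% (shape 1) heal by then. For those among them who are seen early, a gap of at most about a month must be filled by extrapolation.

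**The case against.** **The size is assumed, and it is zero under the plan's own premise.** This stands. With 90% healed in both arms and matching healing times there is no bias, and nothing in the documents supports a large difference in duration. It limits the weight of the point. It does not remove it, because the SAP compares time to healing and the economic method should remain valid if a difference appears.

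**A reader might infer that the window will reverse the QALY result against the faster arm.** The documents do not support that. The reversal above needs a 2-week gap, which is more than any restricted scenario gives even at 90% versus 80%, and it needs equal utility during treatment. The shoe's rationale is the opposite: treatment "without limiting ambulatory activity with its associated negative consequences for physical, mental and social health". The two values that change sign, +0.004 and -0.025, are about 0.1-0.2 and 0.5-1.0 assumed standard errors from zero.

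**A reader might also infer that nobody who fails to heal has a treatment end.** That is too strong. SAP 3.2, 4.3 and 4.4 recognise refusal, discontinuation and withdrawal, and a participant who stops treatment unhealed has a treatment-end date in the ordinary sense. The gap concerns those still unhealed and on treatment. Under the assumed curves they are at most 4% at week 24 (0.2 × 0.2, shape 1, in the 80% arm).

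**The SAP paragraph is an outline, so this is only missing detail.** This holds in part, since no QALY formula is given. But a horizon is stated, and applying it as written produces unequal periods.

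**A common cut-off creates its own asymmetry.** True: slow healers then contribute less time after treatment, so late ulcers and their costs are counted less. This is why the SAP's window should be retained as a sensitivity analysis.

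**Conclusion.** The point holds in conditional form. The cost-utility window has no common length, and its length depends on a post-randomisation outcome. If mean treatment duration differs between arms, the faster-healing arm's QALY difference is biased by -u_h·d/52 relative to a 52-week horizon, assuming equal utility after treatment. Costs also run longer in the slower arm, so the effect on cost per QALY cannot be signed.

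All magnitudes rest on assumed utilities, standard deviations and healing curves. The upper figure of 1.4 standard errors combines extrapolated tails at shape 1 with the highest utility, the smallest SD and the largest sample. Separately, the economic paragraph lacks a date rule for participants still unhealed and on treatment. This should be changed, because the remedy is cheap and is best fixed before outcome data are seen.

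**What to change.** In SAP 6.1.2:
- Make the base-case cost-utility analysis use one common, pre-stated horizon for all randomised participants, for example 12 months from treatment start (the SAP's own origin) or from randomisation, and state which.
- Compute QALYs as the area under the EQ-5D-5L curve by actual assessment date. Interpolate to the cut-off, and carry the last value forward over the short gap when the last assessment falls before it.
- Cut dated costs and sick leave on the same day, and pro-rate self-reported items that span it.
- Use multiple imputation for participants without treatment-end visits, including those still unhealed and on treatment.
- Keep the window anchored on treatment end as a sensitivity analysis, so that effects up to 12 months after treatment are still reported. State there which date applies to participants still on treatment.

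The cost is SAP text and some analysis work, with no new data collection. The downsides are that less post-treatment time is counted for slow healers in the base case. Their EQ-5D-5L is interpolated over a longer gap between week 4 and one month after treatment end, some early healers need short extrapolation, and self-reported costs can only be apportioned approximately.

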6.1.3 SAFETY ANALYSES

Safety endpoints during the treatment period will be reported as summary statics (number and percentage) per study group. They will be categorized as AE, SAE, ADE and SADE (see point 5.3 above) and the proportions will be compared between the study groups with statistical tests for nominal scale data, that is, Chi-square test and presenting exact p-values and two-sided 95% CI.

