Study protocol

**Sealed Therapeutic Shoe vs. Total Contact Cast as Treatment of Diabetic
Foot Ulcers: a Multicenter RCT**

Clinical Trial Registration Number: Unique Protocol ID: 18RS6667

Date: 9 September 2019

Background

Approximately 19-34 % of all people with diabetes will at some time in life develop a diabetic foot ulcer (DFU).¹ People with diabetes are especially prone to develop foot ulcers because of different diabetic complications, especially angiopathy and peripheral neuropathy.

The DFUs are often hard to heal and the treatment is long-lasting. The DFUs result in lower physical and mental quality of life and affects social relationships.² The treatment is also very costly,^{1,3} it has been estimated that 25-50 % of diabetic inpatient care is related to DFUs.⁴ Despite extensive treatment, all DFUs do not heal but some end in amputation. People with diabetes are at a 25-fold risk of amputation and every 20 second a person somewhere in the world has the foot amputated because of diabetes.⁵ 85 % of these amputations are preceded by a foot ulcer⁶ and many of these ulcers and amputation could have been prevented.⁷

Total contact cast (TCC) as gold standard treatment of DFUs

Plantar DFUs often are the result of a combination of foot deformities that increase plantar pressures when the person walks and that the person keeps walking despite high pressure and ulcers because he or she has lost sensation in the feet because of sensory neuropathy. Literature reviews and international guidelines^{8,9} recommend non-removable knee-high offloading devices, for example, a total contact cast (TCC) to treat plantar DFUs, as this offloads the ulcer from mechanical loading all day and night. Still, TCC is not accepted by all patients and is contraindicated in a number of cases because of negative side-effects. Most of these side-effects are the consequences of immobilizing the ankle joint, which impairs gait and results in lower ambulatory activity. For example, side-effects include reduction of joint flexibility, weight gain, muscle atrophy, sick leave from work and social isolation.¹⁰ In addition, a TCC can give secondary ulcers why weekly visits to the hospital is necessary to change casts. For these reasons, TCC is only used for a minority of the patients for whom it could be beneficial, despite being the gold standard treatment.¹¹

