1.2 HYPOTHESES AND OBJECTIVES

The overarching objective is to evaluate whether sealed shoe can heal DFU at least as effectively as TCC, but with fewer adverse events during the treatment period, better long-term effects and to a lower cost.

Specific objectives

Objective 1. To investigate whether a sealed shoe can heal DFUs at least as effectively as TCC (non-inferiority, one-sided hypothesis testing).

Objective 2. To investigate whether there is a difference in adverse events during the treatment period with sealed shoe and TCC (superiority, two-sided hypothesis testing).

Objective 3. To investigate whether there is a difference in long-term effects (up to 12 months after end of treatment) with sealed shoe and TCC (superiority, two-sided hypothesis testing).

Objective 4. To investigate whether there is a difference in health economic outcomes between treatment with sealed shoe and TCC (superiority, two-sided hypothesis testing).

The null hypotheses are that a sealed therapeutic shoe does not heal DFUs at effectively as TCC, and that there are no differences between sealed shoe and TCC in side-effects, long-term effects and health economic outcomes.

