3.2 ADHERENCE AND PROTOCOL DEVIATIONS

Adherence to the interventions (sealed shoe and TCC) is defined as continuous use of the devices during the treatment period. If a person treated with TCC removes the device on one or more occasions or refuses to continue treatment this will be considered non-adherence. If a person treated with a sealed shoe removes the device (assessed by inspecting if the seal has been broken) on one or more occasions or refuses to continue treatment this will be considered non-adherence.

Non-adherence will be presented per type of non-adherence and frequency. All types of non-adherence will be presented as number and percentage. In addition, removal of devices will be presented as means and standard deviation.

A protocol deviation is defined as a failure to adhere to the protocol such as the wrong intervention being administered, incorrect data being collected and documented, errors in applying inclusion/exclusion criteria or missed follow-up visits. This will be presented as number and type, per study group.

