3.3 ANALYSIS POPULATIONS

The primary outcome (ulcer healing) will be analyzed both on the ITT dataset, that is, on all randomized participants, and on the per protocol dataset, including only patients who were exposed to the intended intervention at least 80% of the treatment days, as judged per above (point 3.2). Secondary outcomes (including adverse events and adverse device effects) will only be analyzed on the ITT dataset.

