4.4 WITHDRAW / FOLLOW-UP

There are several timings of possible withdrawal/lost to follow-up: before base-line assessment, before the intervention has been administered, during the intervention period, and before each follow-up assessment. Reasons include, but are not restricted to, clinical reasons, death, refusal to continue treatment or follow-up, unable to make contact with the participant, etc.

Number of participants, reasons and timing of withdrawal/lost to follow-up will be presented by intervention arm in a CONSORT flow diagram (point 4.3)

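### Adverse events are compared as percentages over a period that, for healed participants, ends at their own healing, so the comparison alone cannot separate device risk from length of treatment

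*SAP*

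**What the plan says.** Objective 2 in SAP 1.2 is: "To investigate whether there is a difference in adverse events during the treatment period with sealed shoe and TCC (superiority, two-sided hypothesis testing". SAP 6.1.3 gives the analysis: "Safety endpoints during the treatment period will be reported as summary statics (number and percentage) per study group". Events are sorted into AE, SAE, ADE and SADE, and "the proportions will be compared between the study groups with statistical tests for nominal scale data, that is, Chi-square test". SAP 3.3 sets the population: "Secondary outcomes (including adverse events and adverse device effects) will only be analyzed on the ITT dataset".

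The length of the treatment period comes from the Protocol, Data collection, which schedules the later physiotherapist visits "1, 6 and 12 months after healing (when treatment is ended". A healed participant's period therefore stops at that participant's own healing date.

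Two other groups are foreseen without a closing date for safety. Under SAP 3.2, if a participant "refuses to continue treatment this will be considered non-adherence". SAP 4.4 allows for withdrawal "during the intervention period, and before each follow-up assessment". Neither section says whether adverse events after that point still count, and no section says when the window closes for an ulcer that does not heal.

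For adverse events, neither document plans person-time, an incidence rate, time to first event, a fixed window or a summary of exposure. SAP 6.1.2 reserves survival methods for time to healing and ulcer recurrence.

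**The concern.** Time at risk is set by the efficacy outcome. If one arm heals more slowly, its participants wear the device longer and more of them will have an event, even when the risk in any given week is the same. The plan itself allows for this: time to healing is compared between arms as an outcome, and the non-inferiority design lets the shoe heal somewhat less often and still succeed.

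At stake is the reading of Objective 2, which supports the overall aim of showing fewer adverse events with the shoe. A difference in percentages could come from the device, from the length of treatment, or from both. The subgroup analyses of adverse events in SAP 6.1.5 inherit the same ambiguity.

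**Working it through.** The documents give no event rate, exposure time or power for the safety comparison, so there is no planned figure to reproduce.

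**Inputs from the documents:** 90% healed at 12 weeks in both arms and a 10-point non-inferiority limit (SAP 2.3); 56 per arm at the early recruitment stop and 150/2 = 75 per arm at the target (SAP 2.3); two-sided 5% tests for secondary outcomes (SAP 3.1).

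**Assumptions:** constant healing rate h; constant event rate r, the same in both arms; time counted to healing or week 12, whichever is first; the percentage means participants with at least one event, which SAP 6.1.3 does not spell out.

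**Step 1, time on device.** h = −ln(1 − p)/12 and mean time to week 12 = p/h.
- p = 0.90: h = 0.1919 per week; mean = 0.90/0.1919 = 4.69 weeks.
- p = 0.80: h = 0.1341 per week; mean = 0.80/0.1341 = 5.96 weeks.
- Ratio 5.96/4.69 = 1.27.

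**Step 2, participants with an event.** P = r/(r + h) × (1 − exp(−12(r + h))).

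| Rate per week, both arms | 90% healed | 80% healed | Ratio |
|---|---|---|---|
| 0.05 | 0.2067 × 0.945 = 19.5% | 0.2716 × 0.890 = 24.2% | 1.24 |
| 0.10 | 0.3426 × 0.970 = 33.2% | 0.4271 × 0.940 = 40.1% | 1.21 |

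At 56 per arm the first row is a gap of 0.047 × 56 ≈ 2.6 participants.

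**Step 3, effect on the test.** In 4,000 simulated trials per setting, with equal weekly risks of 5% and 10% and 90% v 80% healed, chi-square rejected in 9.0% and 11.6% of trials at 56 per arm, and in 10.9% and 15.0% at 75 per arm. A direct binomial calculation from the Step 2 percentages agrees (9.3% and 11.7%; 10.5% and 14.5%). At a 2% weekly risk the figure is only 7–8%. A rate-ratio test on the same simulated data rejected in 2–5%.

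**Step 4, range.**
- Same healing pattern in both arms at 90%: 4.69 weeks each, and no distortion.
- 90% healed at week 12 in both arms, but one heals later (Weibull shape 1 v 2): 4.7 v 6.8 weeks, and about 20% v 28% with an event at 5% weekly risk. Equal healing at week 12 is therefore not enough to remove the problem.
- Time counted to healing with no cap at week 12: means 1/h = 5.21 and 7.46 weeks, and 20.7% v 27.2% at r = 0.05. The undefined window for unhealed ulcers thus changes the result.

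**The case against.** The strongest reply is that the percentage per course of treatment is what patients experience. A device that takes longer to heal an ulcer does expose them for longer, and the objective is worded in terms of the treatment period. This stands, and it is a reason to keep the planned comparison. A reader might go further and conclude that Objective 2 cannot be judged from this test at all. The documents do not support that: the test answers a question about the whole course, but not one about risk per week.

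A reader might also infer that the period ends at refusal, so that a cast abandoned because it causes harm would look safer. The Protocol background does say that "TCC is not accepted by all patients and is contraindicated in a number of cases because of negative side-effects", but this concerns acceptance in practice, not drop-out among consenting participants. No section closes the safety window at refusal. A harm that leads someone to give up the device is itself a device effect under SAP 5.3.1, so that participant already counts. If 20% of the cast arm stopped at week 2 for unrelated reasons, and only events on the device counted, 19.5% would fall to 0.8 × 19.5 + 0.2 × 7.9 = 17.2% at r = 0.05. That rests on a closing rule that the SAP does not state.

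Replacing the percentages with a rate per device-week could mislead the other way. Suppose equal risk is confined to weeks 1–2. With the healing rates above, expected events are in the ratio 1.06 (80% v 90% healed) while time on device is in the ratio 1.27. The rate ratio is then 1.06/1.27 ≈ 0.83, and the slower-healing arm looks safer. At 0.10 per week the percentages are almost equal (16.0% v 15.2%).

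There is partial mitigation. Skin complications, gait, balance and other Table 1 measures are compared at a fixed 4-week visit, and the time-to-healing analysis will reveal a difference in duration. Neither covers the AE/SAE/ADE/SADE comparison.

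**Conclusion.** The point holds as a minor one. SAP 6.1.3 plans a single safety comparison that mixes risk per week with length of treatment, and it leaves the window undefined for participants who refuse or do not heal. The distortion is zero if healing patterns match. At the non-inferiority limit it is modest: a ratio of about 1.2, and a chi-square rejection rate of about 9–15% at weekly risks of 5–10%. These sizes rest on assumed constant rates and an assumed cap at week 12. The direction cannot be predicted, because it depends on which arm is treated for longer. The primary endpoint is unaffected.

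**What to change.** In SAP 6.1.3:

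- Keep the number and percentage per arm with the chi-square test.
- State when the safety window opens and closes for healed, unhealed and refusing participants.
- Report weeks on device by arm.
- Beside the percentages, add an exposure-adjusted comparison of ADE and SADE: time to first event, or rate per device-week with a 95% CI. If a single rate is used, note that it assumes roughly constant risk and can mislead if events cluster soon after fitting.
- Count the selected AE/SAE (death, amputation, acute Charcot foot) for all randomised participants to one fixed time from randomisation.

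The cost is SAP wording, a little more analysis, and two safety measures to interpret together. The per-protocol rule in SAP 3.3 already needs a count of treatment days, and visits take place once or twice a week. Those visits record whether a seal was broken, not how long the shoe was off, so weeks on device will approximate actual wear.
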